3. OBJECTIVES

This prospective, single-arm, open-label study will be conducted in patients with newly diagnosed GBM who have completed standard of care radiation therapy together with concomitant TMZ. In this protocol, we propose to combine **TTFields** (utilizing the Optune System) with **pembrolizumab** during the adjuvant **TMZ** treatment phase for newly diagnosed GBM. We hypothesize that TTFields combined with TMZ will elicit anti-mitotic effects on proliferative cancer cells and also significantly augment recruitment of immune effector cells specific for glioma cells to the tumor microenvironment where pembrolizumab, a PD1 inhibitor, further potentiates the glioma-specific immune reaction to achieve a synergistic therapeutic effect.

3.1 Primary Objectives

To determine whether the triple combination (TTFields, temozolomide, pembrolizumab) increases PFS in patients with newly diagnosed GBM as compared to historical control data (TTFields, temozolomide) in the phase 3 registration EF-14 study.

3.2 Secondary Objectives

- 1. To determine toxicity and tolerability of the triple combination in newly diagnosed GBM patients
- 2. To determine OS and RR of the triple combination in newly diagnosed GBM as compared to historical data in the EF14 study.
- 3. To determine whether pembrolizumab augments TTFields-initiated glioma-specific immune reaction.

3.3 Exploratory Objectives

- 1. Metabolomics signature of immune activation by TTFields and TTFields + pembrolizumab in serum and urine.
- 2. To determine if mutation burden, when available from standard of care genomics analysis, in primary tumor samples correlates with response to pembrolizumab in the presence of TTFields.
- 3. To determine if intratumoral expression of PD-L1 correlates with response to pembrolizumab in the presence of TTFields.

4. PATIENT SELECTION

4.1 Inclusion Criteria

- 1) Histologic confirmation of glioblastoma, WHO Grade IV (GBM variants are allowed).
- 2) MGMT methylation status if available (indeterminate methylation status will be considered unmethylated).
- 3) Karnofsky performance status (KPS) \geq 70%.
- 4) Patients must be at least 18 years of age.
- 5) Received maximal safe resection (biopsy only allowed) and radiotherapy concomitant with temozolomide:
 - a. Gliadel wafers placement at the time of surgical resection is allowed.
 - b. Any additional treatment directed at GBM will be considered exclusionary.
 - c. Minimum dose for concomitant radiotherapy is 40 Gy.
- 6) Candidate for adjuvant high dose temozolomide and Optune therapy.
- 7) Life expectancy of at least 3 months.
- 8) Adequate bone marrow and organ function as defined below:
 - a. ANC > 1.500/mcL
 - b. Platelets > 100,000/mcL
 - c. Hemoglobin ≥ 9 g/dL or ≥ 5.6 mmol/L (transfusion is allowed)
 - d. Serum creatinine \leq 1.5 x IULN OR creatinine clearance by Cockcroft-Gault \geq 60 mL/min for patients with serum creatinine > 1.5 x IULN
 - e. Serum total bilirubin \leq 1.5 x IULN OR direct bilirubin \leq IULN for patients with total bilirubin > 1.5 x IULN
 - f. AST (SGOT) and ALT (SGPT) $\leq 3 \times IULN$
- 9) Participants of childbearing age must use effective contraception:
 - Women of childbearing potential (WOCBP) must be using a highly effective method of contraception to avoid pregnancy throughout the study and for at least 24 weeks after the last dose of study drug to minimize the risk of pregnancy. Prior to study enrollment, women of childbearing potential must be advised of the importance of avoiding pregnancy during trial participation and the potential risk factors for an unintentional pregnancy. Refer to Appendix D for guidance on highly effective contraceptive methods.
 - WOCBP include any woman who has experienced menarche and who has not undergone successful surgical sterilization (hysterectomy, bilateral tubal ligation or oophorectomy) or who is not post-menopausal. Post-menopause is defined as:

- Amenorrhea that has lasted for ≥ 12 consecutive months without another cause, or
- For women with irregular menstrual periods who are taking hormone replacement therapy (HRT), a documented serum follicle-stimulating hormone (FSH) level of greater than 35 mIU/mL.
- Males with female partners of childbearing potential must agree to use physician-approved contraceptive methods (*e.g.*, abstinence, condoms, vasectomy) throughout the study and should avoid conceiving children for 24 weeks following the last dose of study drug.
- 10) Ability of the patient to understand and willingness to sign an IRB approved written informed consent document
- 11) Steroid dose equivalent to dexamethasone dose of ≤ 4mg daily at the time of starting adjuvant treatment
- 12) Optune and temozolomide treatment start date will be at least 4 weeks but not more than 6 weeks from the later of last dose of concomitant temozolomide or radiotherapy. Although Optune and temozolomide should be started simultaneously, it is not required as long as both are started within this time frame.

4.2 Exclusion Criteria

- 1. Prior treatment with anti-angiogenic agents including bevacizumab.
- 2. History of other malignancy that, in the primary oncologist's estimation, has a higher risk of recurrence or death than the study-related cancer at the time of study participation.
- 3. Prior treatment with an anti-PD-1, anti-PD-L1, anti-PD-L2, anti-CD137, or anti-cytotoxic T-lymphocyte-associated antigen-4 (CTLA-4) antibody (including ipilimumab or any other antibody or drug specifically targeting T-cell co-stimulation or checkpoint pathways).
- 4. Progressive disease (according to RANO criteria). Advanced imaging is allowed to further investigate suspected pseudoprogression if deemed necessary.
- 5. Actively participating in another clinical treatment trial intended to treat GBM.
- 6. Multifocal gliomas defined as distinct tumors that do not have overlapping T2/FLAIR signal.
- 7. Presence of leptomeningeal metastases.
- 8. Implanted pacemaker, programmable shunts, defibrillator, deep brain stimulator, other implanted electronic devices in the brain, or documented clinically significant arrhythmias.
- 9. Tumor is entirely located in the infra-tentorial region.
- 10. History of hypersensitivity reactions or allergies to hydrogels and/or compounds of similar chemical or biologic composition to Temozolomide and Pembrolizumab.

- 11. Steroid dose equivalent to > 4 mg dexamethasone at the time of starting adjuvant therapy.
- 12. History of immunodeficiency or is receiving any form of immunosuppressive therapy within 7 days prior to the first dose of trial treatment (with the exception of daily dexamethasone ≤ 4 mg).
- 13. Uncontrolled intercurrent illness including, but not limited to, ongoing or active infection, symptomatic congestive heart failure, unstable angina pectoris, cardiac arrhythmia, uncontrolled hypertension, or psychiatric illness/social situations that would limit compliance with study requirements.
- 14. History of active autoimmune disease requiring systemic treatment within the past 2 years (i.e. with use of disease modifying agents, corticosteroids, or immunosuppressive drugs). Replacement therapy (e.g., thyroxine, insulin, or physiologic corticosteroid replacement therapy for adrenal or pituitary insufficiency, etc.) is not considered a form of systemic treatment.
- 15. History of (non-infectious) pneumonitis that required steroids or current pneumonitis.
- 16. Pregnant and/or breastfeeding. Patient must have a negative serum or urine pregnancy test within 72 hours of study entry.
- 17. Females or males of childbearing potential who are unwilling or unable to use an acceptable method to avoid pregnancy for the entire study period and for at least 24 weeks after the last dose of study drug.
- 18. Known active hepatitis B (e.g., HBsAg reactive) or hepatitis C (e.g., HCV RNA [qualitative] is detected) infection.
- 19. Known history of active TB (bacillus tuberculosis).
- 20. Known history of HIV (HIV 1/2 antibodies).

4.3 Inclusion of Women and Minorities

Both men and women and members of all races and ethnic groups are eligible for this trial.

5. SUBJECT RECRUITMENT AND REGISTRATION PROCEDURES

Potential subjects will be recruited to this study from the outpatient clinic after confirmation of tumor pathology when patients are seen to discuss diagnosis, prognosis and treatment options which may include participation in a clinical trial. If a patient is a potential candidate and interested in more information about a specific trial, the Physician-Investigator and/or the research coordinator will discuss the trial further as part of the consent process. All potential subjects will be seen by a study investigator and will be required to sign a written informed consent prior to

being registered on this protocol. Every effort will be made to answer questions raised by the patient and their family or advocate regarding the protocol and alternative therapies prior to asking the patient to sign the consent form. Subjects will be registered after the completion of radiation and concomitant TMZ. MGMT status is not required to sign consent but should be confirmed prior to study registration if feasible (indeterminate methylation status will be considered unmethylated). Both men and women and members of all races and ethnic groups are eligible for this trial.

5.1 Subject Registration in the University of Florida Cancer Center Database

All study subjects will be registered through OnCore at the University of Florida. Each subject will be identified with a unique patient number (UPN) for this study and by first, middle, and last initials. If the subject has no middle initial, a dash will be used on the case report forms (CRFs). All data will be recorded with this UPN on the appropriate CRFs.

6. TREATMENT PLAN

Patients with newly-diagnosed GBM who undergo maximal safe resection (biopsy alone is eligible) followed by chemoradiation consisting of concomitant TMZ 75mg/m² daily and RT with minimal RT dose of 40gy will be eligible for this trial. MGMT methylation status will be recorded.

Four weeks (+7/-14 days) after completing chemoradiation, patients will undergo baseline standard of care MRI. Four to six weeks after finishing chemoradiation, patients will start monthly cycles of adjuvant TMZ. A minimum of 6 and maximum of 12 cycles of adjuvant TMZ will be given depending on tolerability and toxicity.

Treatment with Optune will start at approximately the same time as the first cycle of adjuvant TMZ and continue until second disease progression or a maximum of 2 years. Urine specimens will be collected as well as peripheral blood mononuclear cells (PBMC) will be obtained and cryopreserved at time points specified. No sooner than 3 weeks after starting Optune therapy, patients will begin open-label treatment with pembrolizumab 200mg IV every 3 weeks until first disease progression or unacceptable toxicities or 2 years, whichever comes first.

At first progression, patients will be allowed to continue with Optune therapy combined with any other therapy, which may include pembrolizumab, per standard of care at the discretion of the treating physician. Surgical resection or biopsy of first recurrent tumor for confirmation of recurrence is allowed within the protocol.

For correlative studies, flash frozen tumor tissues, where available, will be used to prime dendritic cells. Intratumoral PD-1 expression will also be determined by IHC using FFPE slides. Research blood will be drawn prior to starting adjuvant therapy and within approximately 1 week before the first dose of pembrolizumab. Subsequently research blood will be drawn prior to the second dose of pembrolizumab, and at approximately 2-, 4-, 6-, 12-, and 24-months (+/- 2 weeks) post-pembrolizumab dosing. Urine samples will be obtained at the same time points as research blood. If there is evidence of progression, however, a final research blood draw and urine sample will be obtained within 30 (+/- 7) days of progression and no further research blood draw and urine specimen will be performed (unless the patient continues on Optune therapy to second progression as detailed in the paragraph above). Research blood will also be collected before resection or

biopsy, when possible. Mutation burden, when available, will be obtained from next gene sequencing analysis per standard of care.

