10.1 Primary Endpoint

Our primary endpoint is progression-free survival time from enrollment to progression or death or censoring, whichever occurs first, with the goal of determining whether the triple combination treatment increases PFS in newly diagnosed GBM patients when compared to TTFields+TMZ historical control patients from the EF-14 study. We will use one-sample log-rank test to compare PFS between the triple combination arm relative to the historical control arm.

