10.3 Sample Size Considerations

To determine if the proposed sample size of 24 patients enrolled in the triple combination arm will allow us to detect a clinically relevant improvement in median PFS relative to the median PFS of 6.7 months observed in the historical control arm, we assumed an accrual period of 12 months, an accrual rate of 2 patients per month, an additional 18 months of follow-up after the end of accrual, and proportional hazards. After confirming that the Weibull distribution could reasonably be used to characterize PFS times in the historical control arm, we estimated the Weibull shape parameter k from the historical control PFS curve. The shape parameter k determines if the hazard rate underlying a survival curve is accelerating over time (k>1), constant over time (k=1; identical to exponential survival), or decelerating over time (k<1). Based on a shape parameter estimate of k=0.88 with empirical 95% confidence interval (0.82,0.95) obtained via simulation of the historical control data, our proposed sample size of 24 patients in the triple combination arm should allow us to detect in improvement in PFS of 6 to 8 months with 80% power and a 1-sided significance level of 0.05 (detectable effect size methodology from Wu and Xiong, 2014 [69]).

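### The primary PFS test against EF-14 makes no use of MGMT status, so a systematic difference in MGMT mix would be read as a pembrolizumab effect; prespecify an MGMT-standardised analysis beside it.

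*Combined protocol and SAP*

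**What the plan says.** The primary analysis is stated in section 10.1: "We will use one-sample log-rank test to compare PFS between the triple combination arm relative to the historical control arm". No stratification, covariate, matching or sensitivity analysis accompanies it. Section 10.2 treats OS and radiographic response the same way.

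Section 10.3 plans the trial on a single historical reference: the "median PFS of 6.7 months observed in the historical control arm" and one Weibull shape ("we estimated the Weibull shape parameter k from the historical control PFS curve"), with k = 0.88 (95% interval 0.82 to 0.95).

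MGMT appears in three places. Section 6 says "MGMT methylation status will be recorded". Section 4.1 lists it only if available, with the rule that "indeterminate methylation status will be considered unmethylated". Section 5 wants it confirmed before registration, if feasible, and repeats that rule. Indeterminate results therefore have a coding rule and absent results have none. Section 10.4 mentions models that bring in clinical and molecular characteristics, but for response signatures, not for the PFS comparison.

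**The concern.** A one-sample log-rank test compares observed events with those expected had the 24 patients followed the historical curve. If MGMT methylation is prognostic for PFS and the trial's source population has a different methylated share from EF-14, the expected count is wrong for reasons unrelated to the drug. Randomisation would protect against this; here nothing does.

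The two sources could plausibly differ. Section 5.1 registers all subjects through one university's system, while section 2.5 describes EF-14 as 695 patients at 83 centres. The direction of any difference is unknown. A higher methylated share risks a false claim of benefit; a lower share risks missing a real one. The plan collects the variable that could separate these explanations but does not use it in the comparison that carries the conclusion.

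**Working it through.** **Inputs from section 10.3.** n = 24; one-sided alpha 0.05; 80% power; historical median 6.7 months; k = 0.88 (0.82 to 0.95); 12 months' accrual at 2 per month; 18 months' further follow-up.

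**Inputs assumed, not in the documents.** EF-14 methylated share 35–40%; PFS hazard ratio, methylated vs unmethylated, 0.5 to 0.7.

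**1. The plan's own figure.** The statistic is Z = (O − E)/√E, where E is the sum over patients of the null cumulative hazard (ln 2/6.7^k)·X^k at follow-up time X. Solving for 80% power gives detectable gains in median PFS of 5.9 months (k = 0.95), 6.7 (k = 0.88) and 7.6 (k = 0.82). At k = 0.88 the treatment hazard ratio is 0.5418, so the median is 6.7 × 0.5418^(−1/0.88) ≈ 13.4 months. This reproduces the stated "improvement in PFS of 6 to 8 months with 80% power and a 1-sided significance level of 0.05".

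**2. A two-stratum null with the same overall median.** For a 40% share and hazard ratio 0.5, set

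0.4·exp(−0.5·λ·6.7^0.88) + 0.6·exp(−λ·6.7^0.88) = 0.5.

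With x = exp(−0.5·λ·6.7^0.88) this becomes 0.6x² + 0.4x − 0.5 = 0. Then x = 0.638, λ·6.7^0.88 = −2·ln(0.638) ≈ 0.897 and, since 6.7^0.88 ≈ 5.33, λ ≈ 0.168. With no drug effect, raising the share to 50% moves the median to about 7.3 months, and 60% moves it to about 7.9.

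**3. False-positive rate of the unadjusted test.** This was simulated with no pembrolizumab effect, an EF-14 share of 40%, and E from the overall curve. The first figure uses variance E; the second uses (O + E)/2, since section 10.1 names neither.

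| PFS hazard ratio, methylated vs unmethylated | Same mix | +10 points | +20 points |
|---|---|---|---|
| 0.5 | 3.8% / 5.1% | 7.3% / 9.4% | 12.6% / 15.7% |
| 0.6 | 3.8% / 5.1% | 6.4% / 8.3% | 9.7% / 12.3% |
| 0.7 | 3.8% / 5.1% | 5.4% / 7.2% | 7.5% / 9.8% |

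With a 35% share the results barely change. Doubling needs a shift of 11–12, 14–15 and 20–21 points at hazard ratios 0.5, 0.6 and 0.7. Tripling needs 18–20, 24–26 and 34–37 points.

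**4. Fewer methylated patients.** At −10 points the error falls to about 1.6–2.5% over hazard ratios 0.5 to 0.7 (variance E). At a treatment hazard ratio of 0.55, power falls from about 0.75–0.79 at equal mix to about 0.67–0.75.

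**5. MGMT-specific expected hazards.** With E summed from stratum curves, the error is 3.7–3.9% (variance E) or 5.0–5.2% (mean variance) at shifts of 0, +10 and +20 points. Power at treatment hazard ratio 0.55 is about 0.80 at equal mix and 0.81 at −10 points.

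**6. Chance imbalance.** The 3.8% at equal mix already includes binomial variation in the number methylated. Conditional on the observed mix, the picture differs. With 40% expected and hazard ratio 0.5, the error is 3.4% / 4.8% if 10 of 24 are methylated and 10.6% / 13.5% if 14 of 24 are.

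**7. Miscoding.** Suppose 15% of methylated patients are coded unmethylated in the trial only (hazard ratio 0.5, variance E). The MGMT-specific test then has error of about 6% with no shift. At +10 points it is 7.0–7.5%, about the same as the unadjusted test. At +20 points it is 8.0–8.5%, against 12.6–12.9% unadjusted. With the same miscoding in both data sets and no shift it is 3.9%.

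**The case against.** The strongest reply is that the effect is conditional throughout. The documents do not say that MGMT is prognostic for PFS, do not give EF-14's mix, and give no reason to expect a higher methylated share here. This stands, and the size must be stated as an assumption with a range.

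A reader might infer that a modest difference in mix doubles or triples the error. That goes too far: at hazard ratio 0.7, 10 points gives about 1.4 times (5.5/3.8), and tripling takes about 20 points even at 0.5. A reader might also argue that 10 points is only one binomial standard deviation with 24 patients (√(0.35 × 0.65/24) = 9.7 points), so chance alone inflates the error. It does not, because that variation is already in the baseline rate. Nor do the documents support the view that every patient is classified, or that the analysis itself must use the Weibull curve: section 10.1 does not specify the reference curve, and the Weibull fit belongs to the sample-size section.

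The remedy has limits too. The rule coding indeterminate as unmethylated raises expected events and so favours the drug if it is applied more often in the trial than in EF-14. Access to EF-14 curves by MGMT is plausible but not shown. The synopsis names the device manufacturer as sponsor and section 3.1 calls EF-14 the registration study, but sections 9.3 and 14.1.1 describe an investigator-initiated trial. Adjusting for MGMT alone would not make the groups comparable. These points argue for placing the adjusted analysis beside the planned test rather than replacing it. They do not remove the gap.

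**Conclusion.** The point holds in conditional form. The primary test and its planning ignore a recorded factor, and no other part of the plan checks or corrects the mix. Assuming a 35–40% EF-14 share and hazard ratio 0.5, the one-sided error goes from about 3.8% to about 7% at +10 points and about 12.6% at +20. At hazard ratio 0.7 it is about 5.5% and 7.7%. A lower share errs the other way and costs up to about 8 points of power at −10 (0.75 to 0.67). These figures describe a systematic difference between sources, which the documents neither show nor exclude. Chance imbalance matters only for how the observed result is read. The change is worth making because it is cheap. Confidence in the size is medium, since both key inputs are assumed.

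**What to change.** In section 10.1, prespecify a second one-sample log-rank analysis of PFS. Each patient's expected cumulative hazard comes from the EF-14 TTFields plus temozolomide PFS curve for that patient's MGMT stratum, and these are summed to give E. Report it beside the unadjusted test, and state that any claim of PFS benefit will be interpreted in light of both. In addition:

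- apply the same coding of missing and indeterminate results to both data sets;
- use the overall EF-14 curve for patients with no MGMT result;
- tabulate the observed MGMT mix against EF-14;
- add a sensitivity analysis that excludes indeterminate results;
- name the variance form of the statistic.

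The cost is a request to the sponsor for EF-14 PFS curves by MGMT status and a paragraph in section 10. There are two downsides. The EF-14 strata are smaller, so their curves are less precise. If methylated patients are coded unmethylated more often in the trial than in EF-14, the adjusted test is itself inflated, which is why the common coding rule and the exclusion analysis are needed.

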6.1 Treatment with Optune

Patients will undergo 24-months of planned treatment with Optune therapy. Therapy will be given as per standard of care (see Section 6.1.1 for recommended use of Optune). 3D mapping and placement maps of recurrent tumors will be completed by the treating physician or Novocure. All device support services (including patients' and families' education of device operation, tips about scalp shaving and array placement, downloading and processing of technical and compliance data, and troubleshooting device malfunction) will be provided by device support specialists employed by Novocure. The goal of treatment compliance for this study is wearing the system for an average of no less than 75% of the time over a 4-week period for as many months as possible. Compliance reports with Optune will be obtained by Novocure's DSS per usual procedures. If a patient's compliance is below 50% over the first and second 4-week periods consecutively from the start of treatment, the patient will be trained on the importance of compliance and any barriers to compliance will be addressed. If a patient's compliance is still below 50% in the third 4-week period, the patient will be removed from study and that subject should be considered non-evaluable for survival analysis and should be replaced. This subject however should remain evaluable for the toxicity and tolerability endpoints as per end of treatment requirement detailed in section 6.6. At the discretion of treating investigators, patients can have an additional treatment break during each 4 week period of no more than 4 days as needed for personal reasons as long as it is estimated that the overall compliance for any 4 week period does not drop below 75% because of the additional break.

